APPENDIX B. BRIGHTON COLLABORATION CRITERIA

Case Definition of Anaphylaxis

For all levels of diagnostic certainty	Level 1 of diagnostic certainty	Level 2 of diagnostic certainty	Level 3 of diagnostic certainty
Anaphylaxis is a clinical syndrome characterized by sudden onset AND rapid progression of signs and symptoms AND involving multiple (≥ 2) organ systems	≥ 1 major dermatological AND ≥ 1 major cardiovascular AND/OR ≥ 1 major respiratory criterion	≥ 1 major cardiovascular AND ≥ 1 major respiratory criterion OR ≥ 1 major cardiovascular OR respiratory criterion AND ≥ 1 minor criterion involving ≥ 1 different system (other than cardiovascular or respiratory systems) OR (≥ 1 major dermatologic) AND (≥ 1 minor cardiovascular AND/OR minor respiratory criterion)	≥ 1 minor cardiovascular OR respiratory criterion AND ≥ 1 minor criterion from each of ≥ 2 different systems/ categories

The case definition should be applied when there is no clear alternative diagnosis for the reported event to account for the combination of symptoms.

Major and Minor Criteria Used in the Case Definition of Anaphylaxis

	Major Criteria	Minor Criteria
Dermatologic or mucosal	
 generalized urticaria (hives) or generalized erythema angioedema*, localized or generalized generalized pruritus with skin rash 	
 generalized pruritus without skin rash generalized prickle sensation localized injection site urticaria red and itchy eyes
Cardiovascular	
 measured hypotension clinical diagnosis of uncompensated shock, indicated by the combination of at least 3 of the following: 
 tachycardia capillary refill time >3 s reduced central pulse volume decreased level of consciousness or loss of consciousness 	
 reduced peripheral circulation as indicated by the combination of at least 2 of 
 tachycardia a capillary refill time of >3 s without hypotension a decreased level of consciousness
Respiratory	
 bilateral wheeze (bronchospasm) stridor upper airway swelling (lip, tongue, throat, uvula, or larynx) respiratory distress—2 or more of the following: 
 tachypnoea increased use of accessory respiratory muscles (sternocleidomastoid, intercostals, etc.) recession cyanosis grunting 	
 persistent dry cough hoarse voice difficulty breathing without wheeze or stridor sensation of throat closure sneezing, rhinorrhea
Gastrointestinal		
 diarrhoea abdominal pain nausea vomiting
Laboratory		Mast cell tryptase elevation $>$ upper normal limit

* Not hereditary angioedema

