4. Investigate mental health characteristics of participants who experience an allergic reaction to the COVID-19 vaccine.
5. Assess psychological impact of allergic reactions to the COVID-19 vaccine and examine changes in stress levels over time.
6. Assess anxiety levels in participants and examine changes in anxiety over time.
7. Assess the proportion of participants who experience no reaction or only a mild reaction (CoFAR Grade 2 or below) to a booster dose of the Pfizer-BioNTech vaccine after previously demonstrating a systemic allergic reaction (CoFAR Grade 2 or 3 reaction regardless of tryptase OR Grade 1 reaction with elevated tryptase [1.2 X baseline plus 2 ng/mL]) to their first full dose of the Pfizer-BioNTech or Moderna COVID-19 vaccine and no allergic reaction or a mild reaction (CoFAR Grade 2 or below) to a subsequent (second) dose of the Pfizer-BioNTech vaccine.
8. Assess the development of autoantibodies after COVID-19 vaccination.

Endpoints:

Primary Endpoint:

1. The proportion of participants who previously demonstrated a systemic allergic reaction (CoFAR Grade 2 or 3 reaction regardless of tryptase OR Grade 1 reaction with elevated tryptase [1.2 X baseline plus 2ng/mL]) to their first full dose of the Pfizer-BioNTech or Moderna COVID-19 vaccine who experience a **systemic allergic reaction** (CoFAR Grade 2 and above reaction regardless of tryptase, or CoFAR grade 1 with elevated tryptase [1.2 X baseline plus 2ng/mL]) within the 3-hour post-vaccine observation period to a subsequent dose of the Pfizer-BioNTech vaccine.

Secondary Endpoints:

2. The proportion of participants who previously demonstrated a systemic allergic reaction (CoFAR Grade 2 or 3 reaction regardless of tryptase OR Grade 1 reaction with elevated tryptase [1.2 X baseline plus 2ng/mL]) to their first full dose of the Pfizer-BioNTech or Moderna COVID-19 vaccine who experience a **severe systemic allergic reaction** (CoFAR grade 3 reaction and above) within the 3-hour post-vaccine observation period to a subsequent dose of the Pfizer-BioNTech vaccine.

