3. The proportion of participants who previously demonstrated a systemic allergic reaction (CoFAR Grade 2 or 3 reaction regardless of tryptase OR Grade 1 reaction with elevated tryptase [1.2 X baseline plus 2ng/mL]) to their first full dose of the Pfizer-BioNTech or Moderna COVID-19 vaccine who experience a **mild-moderate allergic reaction** (CoFAR grade 1 or 2 reaction regardless of tryptase) within the 3-hour post-vaccine observation period to a subsequent dose of the Pfizer-BioNTech vaccine.
4. The proportion of participants who previously demonstrated a systemic allergic reaction (CoFAR Grade 2 or 3 reaction regardless of tryptase OR Grade 1 reaction with elevated tryptase [1.2 X baseline plus 2ng/mL]) to their first full dose of the Pfizer-BioNTech or Moderna COVID-19 vaccine who experience an **anaphylactic reaction** (Levels 1-3) per Brighton Collaboration Criteria within the 3-hour post-vaccine observation period to a subsequent dose of the Pfizer-BioNTech vaccine.
5. The proportion of participants who previously demonstrated a systemic allergic reaction (CoFAR Grade 2 or 3 reaction regardless of tryptase OR Grade 1 reaction with elevated tryptase [1.2 X baseline plus 2ng/mL]) to their first full dose of the Pfizer-BioNTech or Moderna COVID-19 vaccine who experience a systemic allergic reaction (CoFAR grade 2 reaction and above regardless of tryptase, or CoFAR grade 1 with elevated tryptase [1.2 X baseline plus 2ng/mL]) within the 3-hour post-vaccine observation period to a subsequent dose of the Pfizer-BioNTech vaccine compared to the rate of these reactions following placebo administration.

6. The proportion of participants who previously demonstrated a systemic allergic reaction (CoFAR Grade 2 or 3 reaction regardless of tryptase OR Grade 1 reaction with elevated tryptase [1.2 X baseline plus 2ng/mL]) to their first full dose of the Pfizer-BioNTech or Moderna COVID-19 vaccine who develop a lower or higher grade allergic reaction within the 3-hour post-vaccine observation period to a subsequent dose of the Pfizer-BioNTech vaccine.

Exploratory Endpoints:

7. Prevalence of polyethylene glycol (PEG) and severe acute respiratory syndrome coronavirus 2 (SARS-CoV-2) antibodies in each participant at baseline.
8. Changes in anti-PEG and SARS-CoV-2 antibodies in each participant approximately 1 and 5 months after receiving the dose of the Pfizer-BioNTech vaccine administered on study.

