8.2.2 Biospecimen Evaluations

Specimens (blood, urine, and nasal swabs) will be used to assess:

- Overall atopic status
- Pre-existing antibodies to polyethylene glycols (Sample analysis will not be completed prior to vaccination; therefore, results will not be used to assess eligibility.)
- Known mediators of systemic reactions due to mast cell activation (e.g., serum tryptase and urinary leukotrienes, prostaglandins, histamine)
- General markers of an acute inflammatory response (e.g., serum IL-6)
- Activation of the classical and alternative complement pathways
- Contact activation of the kinin system
- Activation of basophils and neutrophils
- Unsupervised proteomics, metabolomics, and whole blood transcriptomics
- Analysis of peripheral blood mononuclear cells (PBMCs) may also be explored to assess for new mechanisms
- Evidence of clonal mast cell disease and genetic variants that may increase the risk and/or severity of allergic reactions (e.g. hereditary alpha tryptasemia, clonal mast cell disease)
- Autoantibodies pre and post COVID-19 vaccination

Specific laboratory studies may include those listed below. Assays may be removed or added based on the number and character of reactions seen within the trial. In addition, the timepoints for the conduct of specific laboratory studies may change from what is specified below.

Specimens will be processed at the Laboratory of Allergic Diseases (LAD), Laboratory of Viral Diseases (LVD), Laboratory of Immune System Biology (LISB), and the Laboratory of Bacteriology at the Rocky Mountain Laboratories at NIAID, the Department of Laboratory Medicine (DLM) at NIH (including send-outs to Mayo Clinic), and the Systemic Autoimmunity Branch at the National Institute of Arthritis and Musculoskeletal and Skin Diseases. Coded specimens will also be sent to collaborators at Yale University, Virginia Commonwealth University, Stanford University, University of North Carolina, University of Pittsburgh, KalVista Pharmaceuticals, Inc., and the US FDA for processing.

Blood/serum/plasma:

The following tests may be performed for all participants:

- Whole blood for genetic analysis of the tryptase locus, c-kit locus, and other genetic variants that might influence the risk and/or severity of allergic reactions (Visit 1, pre-dosing)
- Total IgE (Visit 1, pre-dosing Day 1 only)
- Allergen-specific IgE (Visit 1, pre-dosing)

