9.1 STATISTICAL HYPOTHESIS

The primary goal is estimation of the primary and secondary endpoints, and estimation of the difference in endpoints between the active and placebo vaccines. Statistical hypothesis testing will be done to compare active versus placebo vaccines, but this is secondary to estimation.

The endpoints are as follows, and are defined in greater detail previously in the protocol (sections 1.1 and 3):

Primary Endpoint:

- Proportion with systemic allergic reaction to the active (ie, Pfizer-BioNTech) vaccine dose delivered in this study

Secondary Endpoints:

- Proportion with severe systemic allergic reaction to the COVID-19 vaccine dose delivered in this study
- Proportion with mild/moderate systemic allergic reaction to the COVID-19 vaccine dose delivered in this study
- Proportion with anaphylactic reaction to the COVID-19 vaccine dose delivered in this study
- Proportion with systemic allergic reaction to each study vaccination (i.e. active and placebo/pre- and post-crossover) by arm
- Proportion with more (or less) severe systemic allergic reaction to the COVID-19 vaccine dose delivered in this study than recorded reaction to the first full COVID-19 vaccine dose

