9.4.7 Sub-Group Analyses

The baseline characteristics of the cohort will be described. If the number of enrolled patients is sufficient, endpoints will be analyzed in subgroups (e.g., gender; age; ethnicity; severity of reaction to original vaccine dose; menopausal status for female participants; presence, type, and severity of allergic diseases; laboratory assessments of allergic sensitization and inflammation; history of allergic reactions including cause, severity, and treatment required; presence, type, and levels of anti-PEG antibodies; history of prior SARS-CoV-2 infection; other medical comorbidities; medication use; presence of genetic variants that may influence response to vaccine including but not limited to hereditary alpha tryptasemia; level of inflammatory and immune markers at baseline).

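### The Brighton tryptase criterion ignores baseline, so the anaphylaxis endpoint is partly tied to raised baseline tryptase and analyses of it by that trait are partly circular

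*Combined protocol and SAP*

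**What the plan says.** The protocol has two tryptase rules.

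- **Primary endpoint (Synopsis 1.1 and Section 3).** Tryptase is judged against the participant's own baseline: "CoFAR grade 1 with elevated tryptase [1.2 X baseline plus 2ng/mL]) within the 3-hour post-vaccine observation period". The entry criterion in Section 5.1 uses the same formula.
- **Anaphylaxis endpoint (listed as 4 in the Synopsis, 3 in Section 3).** It counts Brighton Levels 1 to 3 as set out in Appendix B. The only laboratory criterion there, a minor one, is "Mast cell tryptase elevation $>$ upper normal limit". Baseline is not mentioned.

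Appendix B requires at every level a sudden, rapidly progressing syndrome "involving multiple (≥ 2) organ systems". Level 3 needs a minor cardiovascular or respiratory criterion plus minor criteria from at least two other systems or categories.

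The endpoint covers the active dose only. Section 9.1 lists it as "Proportion with anaphylactic reaction to the COVID-19 vaccine dose delivered in this study", and the placebo comparison in Section 9.4.3 uses the CoFAR-based reaction.

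Section 8.2.2 schedules tryptase before dosing and at 35 minutes and 2 hours after each injection. It also provides for testing of "genetic variants that may increase the risk and/or severity of allergic reactions (e.g. hereditary alpha tryptasemia, clonal mast cell disease". If enrollment is sufficient, Section 9.4.7 analyses endpoints by subgroups that include "presence of genetic variants that may influence response to vaccine including but not limited to hereditary alpha tryptasemia" and baseline inflammatory and immune markers. Section 9.4.9 compares baseline mechanistic measures between participants with and without systemic reactions, and does likewise for the other allergic endpoints. No exclusion criterion in Section 5.2 names raised baseline tryptase.

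**The concern.** A tryptase value that is high before the injection and unchanged after it says nothing about a reaction. Under Appendix B it still counts, so participants with such a baseline need fewer clinical signs than others to be classified as anaphylaxis.

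The signs involved are plausible in this trial. Section 2.2 says that anxiety can produce shortness of breath and throat tightness, and a sensation of throat closure is a minor respiratory criterion. Section 8.3 lists nausea, vomiting and diarrhea as expected vaccine events, and each is a minor gastrointestinal criterion.

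At stake is the reading of the subgroup and risk-factor results. More anaphylaxis among participants with raised baseline tryptase would be expected even if they reacted exactly as others do, and it could be reported as a risk factor.

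**Working it through.** **Plan's own figure.** No stated figure depends on this definition. The interval that applies to the endpoint (exact Clopper-Pearson) was checked against Table 5: 2/10 gives 0.025 to 0.556 and 20/100 gives 0.127 to 0.292. Both match.

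**Step 1: the two rules with unchanged tryptase.** Let b be the baseline, the value stay at b, and U be the upper normal limit. The documents do not give U, so 10 to 15 ng/mL is assumed.

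- Appendix B is met whenever b > U.
- The primary-endpoint rule needs b to reach 1.2b + 2. Since b < 1.2b + 2 for every b >= 0, it is never met.
- Example: U = 10, b = 11. Appendix B is met. The other threshold is 1.2 x 11 + 2 = 15.2, so that rule is not.
- The rules coincide at b = (U - 2)/1.2, which is 6.7 ng/mL for U = 10 and 10.8 for U = 15. Above that baseline Appendix B is the looser rule; below it, the stricter.

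**Step 2: one pattern by hand.** Take a minor respiratory and a minor gastrointestinal sign. Two organ systems are involved. Without tryptase, only one further category accompanies the respiratory sign, so Level 3 is not reached. With tryptase there are two, and it is Level 3.

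**Step 3: all patterns.** Seven clinical items (major and minor dermatologic, cardiovascular and respiratory; minor gastrointestinal) give 2^7 = 128 patterns. The two-organ-system requirement is applied, and the laboratory is not counted as an organ system.

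| Tryptase criterion | Patterns at Level 1-3 |
|---|---|
| Not met | 105 of 128 |
| Met | 114 of 128 |
| Met, no clinical sign | no level reached |

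Tryptase decides 114 - 105 = 9 patterns: five become Level 3 and four become Level 2. Level 2 speaks of a different system, while Level 3 speaks of systems or categories. If the laboratory is not allowed to count at Level 2, the total is 112 and tryptase decides 7 patterns, all at Level 3.

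**Step 4: size.** Sign rates are assumed: independent, and identical whether or not baseline is raised. P0 is the Level 1-3 rate with the criterion never met (normal baseline, no rise). P1 is the rate with it always met (raised baseline).

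| Assumed rate, each major / each minor item | P0 | P1 | P1/P0 |
|---|---|---|---|
| 2% / 10% | 1.6% | 5.7% | 3.6 |
| 5% / 20% | 7.9% | 20.1% | 2.5 |
| 10% / 40% | 31.4% | 54.7% | 1.7 |

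Under the narrower Level 2 reading the ratios are 3.5, 2.4 and 1.7.

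**Step 5: true rises.** If an assumed fraction f of normal-baseline participants meets the criterion through a real rise, the ratio is P1/[P0 + f(P1 - P0)]. For f = 25% it is 2.2, 1.8 and 1.5. For f = 50% it is 1.6, 1.4 and 1.3.

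**Step 6: whole cohort.** If 20% of participants had raised baseline (assumed), the overall proportion would rise by 0.20 x (P1 - P0): 0.8, 2.4 and 4.7 percentage points. Table 5's interval at N = 100 with 20% observed is 29.2 - 12.7 = 16.5 points wide.

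**The case against.** The strongest defence is comparability. Section 3 justifies the secondary endpoints partly by comparison with other studies and with CDC data, and the CDC cases in Section 2.2 were classified by Brighton. Changing the definition would weaken that comparison. This stands, and it is why the standard definition should remain the endpoint.

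Second, Appendix B already limits the effect. Every level needs a cardiovascular or respiratory criterion, at least two organ systems, and no clear alternative diagnosis. This also stands: the gap matters only for participants who already have signs in two systems. The alternative-diagnosis clause concerns symptoms, however, and gives no rule for a high baseline tryptase.

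Third, the subgroup analyses depend on enrollment, Section 9.4.7 names no test, and Section 9.4.1 cautions about multiplicity. That limits how firmly a subgroup result would be read. It does not make the comparison less circular.

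A reader might infer three stronger things that the documents do not support.

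- **That an association with hereditary alpha tryptasemia is built in.** This needs carriers to have baseline values above the limit. The protocol gives no limit, no carrier values and no carrier frequency. It shows only that the variant is tested and is a possible subgroup factor.
- **That the vaccine-placebo comparison is distorted.** The criterion would indeed be met after either injection, but the Brighton endpoint is defined for the active dose only.
- **That the multiple is far larger.** Counting only Level 3 from minor signs can give 13-fold at low assumed sign rates. The endpoint is Levels 1 to 3, so major criteria must be included. A false-positive rate for a subgroup test would also presume a test that the plan does not name.

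**Conclusion.** The concern holds in limited form. Appendix B's tryptase criterion lacks the baseline term that the primary endpoint has, so a participant already above the limit meets it without any change and, with signs in two organ systems, reaches Level 2 or 3 more easily. Any analysis of the anaphylaxis endpoint by baseline tryptase is therefore partly circular. The same applies to hereditary alpha tryptasemia only to the extent that carriers are above the limit.

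The size, about 1.7 to 3.6 times, rests on assumed independent and equal sign rates and on no tryptase rise in normal-baseline participants. It is an upper-end contrast within those scenarios, and true rises reduce it. At an assumed 20% share, the effect on the overall proportion is small beside its confidence interval; the subgroup and risk-factor analyses are where it matters. The primary endpoint, sample size, alpha and vaccine-placebo contrast are unaffected. This is a cheap improvement to the plan and does not invalidate the endpoint.

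**What to change.** Keep the unmodified Brighton Levels 1-3 proportion as the secondary endpoint, for comparison with CDC data.

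Add to Sections 9.4.3, 9.4.7 and 9.4.9 a prespecified sensitivity version in which the laboratory criterion counts only if tryptase is above the upper normal limit and also meets 1.2 x the participant's pre-dose baseline + 2 ng/mL. Use this version for any analysis of anaphylaxis by hereditary alpha tryptasemia, clonal mast cell disease or baseline tryptase. An unchanged value can never satisfy it, so the built-in association from constant high tryptase disappears.

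The samples are already scheduled in Section 8.2.2. Because Section 9 says that no separate analysis plan is intended, the wording belongs in the protocol. The cost is a few sentences and two reported versions of the anaphylaxis proportion.
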